9.2. Setting

Patients and Methods

Data was collected from the Baghdad Teaching Hospital rheumatology registry. It captured all patients who have been treated with biologic therapies managed in the rheumatology department. The decision to initiate and maintain the treatment was guided by the American College of Rheumatology (ACR) recommendations.

Study population

Patients included in the study met the American College of Rheumatology/European League Against Rheumatism (EULAR) 2019 criteria for SpA⁶, with at least 1 year of follow-up after starting their first biologic therapy. Exclusion criteria: patients previously or currently treated with other biological treatments.

Hypothesis

There was a small percentage of patients who adhered to Enbrel over 7 years, and there was no difference between the adherent and the nonadherent group in efficacy.

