9. RESEARCH METHODS

9.1. Study Design

- **Retrospective analysis** of patients with SpA that received etanercept from Baghdad Teaching Hospital (Rheumatology Center) from May 2012 through August 2019.
- **Primary objective:** 1 and 7 years adherence of SpA patients on Enbrel.
- **Secondary objective:** The difference in efficacy between the adherent group of patients (who continued Enbrel treatment) and the nonadherent group.

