9.2.1. Inclusion Criteria

Patients met all of the following inclusion criteria to be eligible for inclusion in the study:

1. Diagnosed SpA patients.
2. 18 years of age and older.
3. Did not receive previous other biological treatments.
4. Patients have at least 1 year on Enbrel.

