9.2.2. Exclusion Criteria

Patients meeting any of the following criteria were not included in the study:

1. Had previously used another biological treatments.
2. Use of etanercept for less than 1 year duration.

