9.3. Data Sources

Patients were identified from the rheumatology patient registry with a SpA diagnosis and information was obtained on patient demographics (age, gender), education-level (years), present smoking status, disease duration (years), current MTX and steroid therapy (yes/no), baseline BASDAI, and BASFI and last assessment of baseline BASDAI and BASFI.

Primary Outcomes: was the percentage of patients that have 7 year adherence on Enbrel.

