9.6. Data Analysis

All covariates will be summarized to get information about frequency distribution and mean, median or standard deviation. Numbers and percentages will be provided for dichotomous and polychotomous variables when performing descriptive analysis of categorical data. Means, medians, standard deviations, and interquartile range as appropriate will be provided for continuous variables when performing descriptive analysis of continuous data. Patients will be assessed for first-year adherence (first-year adherence is defined as patients having at least 7 consecutive visits in one year of Enbrel treatment), then the 7-year adherence will be assessed and the percentage of patients that achieve 7-year adherence will be calculated. The difference between adherent and nonadherent groups in baseline visit and last visit BASDAI and BASFI will be assessed for both groups.

The bivariate analysis will be conducted to determine if there is any association between the outcome and the exposure (the covariates). Unadjusted comparisons between groups of covariates and outcomes will be evaluated using appropriate tests: chi-squared test will be used for categorical variables, t-test will be used for continuous variables, and the Kruskal-Wallis test for non-parametric variables; p-values will be generated. The baseline variables considered demographic data, disease duration (years), methotrexate (yes/no), current steroid therapy (yes/no), present smoking (yes/no).

The difference in efficacy between adherent and nonadherent groups by using change from the baseline in BASDAI and BASFI at the last visit will be determined. P-value <0.05 will be considered statistically significant, without multiplicity adjustment for this post-hoc analysis.

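### The exclusion for other biologics is worded in two ways and never dated; if it was judged at data extraction, later switchers drop out and 7-year adherence is probably overstated

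*Combined protocol and SAP*

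**What the plan says.** The combined protocol and SAP states the prior-biologic criterion three times.

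- Section 9.2 (Study population): "Exclusion criteria: patients previously or currently treated with other biological treatments".
- Section 9.2.1, inclusion item 3: "Did not receive previous other biological treatments".
- Section 9.2.2, exclusion item 1: "Had previously used another biological treatments".

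Only the first covers current use, and none carries a reference date. The one time anchor nearby, also in 9.2, describes patients "with at least 1 year of follow-up after starting their first biologic therapy". It is attached to length of follow-up, not to the exclusion.

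Section 9.1 places Enbrel treatment "from May 2012 through August 2019" and describes "the adherent group of patients (who continued Enbrel treatment" as the group to be compared with the nonadherent. Section 9.3 says the primary outcome "was the percentage of patients that have 7 year adherence on Enbrel". Section 6 puts data collection between 1 September and 1 October 2020.

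**The concern.** The study is retrospective, and the extraction falls after the treatment window has closed. By then a patient's later biologic history may already be in the registry, which section 9.2 says covers every biologic-treated patient in the department. Read literally at extraction, *currently* excludes a patient who started Enbrel biologic-naive and has since moved to another biologic. An undated *previously* could also exclude a patient who switched and then stopped the second drug.

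A patient who switched before year 7 did not continue Enbrel and is nonadherent. Removing such patients makes entry to the denominator depend on the outcome being measured. Because the primary result is a single percentage, a reader must be able to reconstruct its denominator, and the present text does not allow that. The make-up of the nonadherent group in the BASDAI and BASFI comparison would change too, in a direction that cannot be determined.

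**Working it through.** **Step 1. The wording side by side.**

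| Section | Previous use excluded | Current use excluded | Date of judgement |
|---|---|---|---|
| 9.2 | yes | yes | none |
| 9.2.1, item 3 | yes | not mentioned | none |
| 9.2.2, item 1 | yes | not mentioned | none |

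The mismatch and the missing date are both in the text.

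**Step 2. Effect on the primary percentage.** The plan gives no expected adherence, switching share or sample size, so it has no figure to reproduce. Section 9.2 hypothesises only that a small percentage adhere over 7 years. Let

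- R = true 7-year adherence among all eligible starters,
- s = share of nonadherers removed by the exclusion,
- a = share of adherers removed by it.

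All three are assumptions. Then

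Reported = R(1 − a) / [R(1 − a) + (1 − R)(1 − s)].

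If status is judged at the start of Enbrel, later switching removes nobody, so a = s = 0 and Reported = R.

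**Step 3. Illustration with a = 0.**

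| R | s = 5% | s = 10% | s = 25% |
|---|---|---|---|
| 10% | 0.1/0.955 = 10.5% | 0.1/0.910 = 11.0% | 0.1/0.775 = 12.9% |
| 30% | 0.3/0.965 = 31.1% | 0.3/0.930 = 32.3% | 0.3/0.825 = 36.4% |

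Nonadherers who stopped Enbrel without starting another biologic are not removed, which limits s.

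**Step 4. Direction.** The formula exceeds R exactly when s > a. With R = 10%:

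- a = 5%, s = 10%: 0.095/(0.095 + 0.810) = 10.5%, upward.
- a = 10%, s = 10%: 0.090/(0.090 + 0.810) = 10.0%, no change.
- a = 10%, s = 5%: 0.090/(0.090 + 0.855) = 9.5%, downward.

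**Step 5. Which of a and s is likely to be larger.** Assume from section 9.1 that no patient started Enbrel before May 2012. A 7-year adherer can then switch no earlier than 1 May 2012 + 7 years = 1 May 2019. That leaves at most about 4 months to 31 August 2019, or about 17 months to 1 October 2020. A nonadherer can also switch before year 7. So s > a is probable, but nothing in the documents proves it.

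**The case against.** The strongest reply is that the harmful reading is the less natural one. In an Enbrel cohort, the reference in 9.2 to the first biologic implies that patients were naive at the start. *Previous* in 9.2.1 and 9.2.2 most naturally means before Enbrel. Section 9.6 lists "current steroid therapy (yes/no), present smoking (yes/no" among the baseline variables, so the plan does use *current* for baseline status. On that usage, a current other biologic means one taken alongside Enbrel at baseline. The enumerated lists also omit current use, and if they govern, much of the problem goes away. Nothing in the documents shows that any switcher was removed, and no switching share is given.

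Most of this stands. The benign reading is plausible and gives zero bias, and the size under the other reading is unknown. The 30% row in particular has no support beyond illustration. What does not follow is that the text is adequate. A plausible inference is not a stated rule, 9.2 is itself a stated exclusion, and nothing says that the lists override it.

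It is also fair to say that dating this criterion will not by itself make the 7-year percentage reproducible. Section 9.6 gives no operational definition of 7-year adherence, and the requirement of at least 1 year on Enbrel is a further selection. Those are separate matters and do not remove this one.

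**Conclusion.** The concern holds as a conditional one and should be fixed. It is certain that the three statements differ and that none is dated. The bias is zero if status was judged at the start of Enbrel. If it was judged later, 7-year adherence is overstated whenever s > a, which is probable given the short time in which a 7-year adherer could switch. That time limit rests on the assumption that no start precedes May 2012. In the illustrations the overstatement runs from 0.5 points (10% to 10.5%) to 6.4 points (30% to 36.4%). These figures rest on assumed values of R and s with a = 0 and do not estimate what happened. No claim is made about 1-year adherence.

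**What to change.** Use one criterion in 9.2, 9.2.1 and 9.2.2: no other biologic before or at the first Enbrel dose. Delete the undated reference to current treatment. State that patients who switch later stay in the denominator and count as nonadherent if they left Enbrel before 7 years. Report the date at which status was judged and the number of patients excluded by this criterion.

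The cost is rewording in three places and one count. Only if later switchers were removed must they be restored and the 7-year percentage re-run; reported adherence may then be lower. That could mean reopening an extraction planned to end on 1 October 2020, because later biologic use is not among the variables listed in 9.3. Recovery may be hard: section 10 describes the data as anonymized, and section 11 says that data on individual patients were not retrieved, although 9.5 describes a structured export to Excel and SPSS. If recovery proves impossible, give the date used and the number excluded as a limitation in 9.8.

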9.2.1. Inclusion Criteria

Patients met all of the following inclusion criteria to be eligible for inclusion in the study:

1. Diagnosed SpA patients.
2. 18 years of age and older.
3. Did not receive previous other biological treatments.
4. Patients have at least 1 year on Enbrel.

9.2.2. Exclusion Criteria

Patients meeting any of the following criteria were not included in the study:

1. Had previously used another biological treatments.
2. Use of etanercept for less than 1 year duration.

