8. RESEARCH QUESTION AND OBJECTIVES

The objective of this study was to evaluate the 1 and 7 years (long-term) adherence of SpA patients on Enbrel and the difference in efficacy between adherent and nonadherent groups.

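### Eligibility requires at least 1 year on Enbrel, so first-year stoppers are missing from the 1-year adherence figure, from the nonadherent efficacy group and, on one reading, from the 7-year figure

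*Combined protocol and SAP*

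**What the plan says.** Section 8 states the aim as to "evaluate the 1 and 7 years (long-term) adherence of SpA patients on Enbrel", and section 9.1 repeats this as the primary objective. Section 9.3 names the primary outcome as the "percentage of patients that have 7 year adherence on Enbrel". None of these statements restricts the target to patients who have already completed a year.

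The eligibility lists do. Section 9.2.1 requires "Patients have at least 1 year on Enbrel", and section 9.2.2 excludes "Use of etanercept for less than 1 year duration".

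The narrative in section 9.2 sets a different condition. It asks for patients "with at least 1 year of follow-up after starting their first biologic therapy", which concerns observation and not treatment. It also excludes patients treated with another biologic, whether in the past or at present. On coverage of the registry it says: "It captured all patients who have been treated with biologic therapies managed in the rheumatology department".

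Section 9.6 defines first-year adherence by attendance: at least 7 consecutive visits in a year of Enbrel treatment. The 7-year percentage is assessed next, but neither its definition nor its denominator is given. For the secondary objective, section 9.1 describes the "adherent group of patients (who continued Enbrel treatment") and compares it with the nonadherent group. Section 9.8 speaks only of missing data.

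**The concern.** A patient who starts Enbrel and stops at month 5 has not continued treatment, and on the description of the groups in section 9.1 is nonadherent. The eligibility lists remove that patient before anything is measured, and no section adds such patients back. Selection into the cohort therefore depends on something very close to the outcome.

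Three results are exposed. The 1-year figure becomes visit attendance among people who stayed on drug for a year, which is not first-year adherence among starters. The 7-year figure may hold only for 1-year completers. The efficacy comparison sets adherent patients against a nonadherent group from which the earliest stoppers have been taken out. A reader of the study report would have no warning, because the objective, the outcome and the limitations section do not mention the restriction.

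**Working it through.** **What the text fixes.** Sections 9.2.1 and 9.2.2 both require at least 1 year of treatment, so an early stopper fails both. The follow-up wording in section 9.2 would, taken alone, keep an early stopper who was still followed and had not switched. One who was now on another biologic would still be excluded by the same section. The three sections therefore do not describe one population.

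**Inputs.** The plan states no sample size, expected adherence or stopping rate, so there is no figure to reproduce. All of the following are assumptions:
- d, the share of starters who stop before 1 year: 5%, 10%, 20%, 30%, 40%.
- v, the share of 1-year completers who meet the 7-visit rule.
- k, the early stoppers' rate of meeting that rule divided by v. With k = 0 none met it; with k = 0.5 they met it at half the completers' rate.
- R, the 7-year percentage in the eligible cohort.

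**1-year figure.** The plan estimates v. Among all starters the value is v × [(1 − d) + d·k], so the inflation factor is 1 / [(1 − d) + d·k].

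**7-year figure, full 7-year follow-up assumed.** If the denominator is all eligible patients, the all-starter value is R × (1 − d) and the factor is 1 / (1 − d). If the denominator is first-year adherers, the factor is [(1 − d) + d·k] / (1 − d).

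| d | 1-year, k = 0 | 1-year, k = 0.5 | 7-year, all eligible | 7-year, first-year adherers, k = 0 | 7-year, first-year adherers, k = 0.5 |
|---|---|---|---|---|---|
| 5% | 1.05 | 1.03 | 1.05 | 1.00 | 1.03 |
| 10% | 1.11 | 1.05 | 1.11 | 1.00 | 1.06 |
| 20% | 1.25 | 1.11 | 1.25 | 1.00 | 1.13 |
| 30% | 1.43 | 1.18 | 1.43 | 1.00 | 1.21 |
| 40% | 1.67 | 1.25 | 1.67 | 1.00 | 1.33 |

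For example, with all eligible patients as denominator, a reported R of 40% corresponds to 38%, 36%, 32%, 28% or 24% of all starters.

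**Nonadherent starters removed from the efficacy comparison.** If the groups are split by 7-year status, the share removed is d / [1 − R(1 − d)]. At R = 40% this is 8%, 16%, 29%, 42% and 53% down the same grid. Over R from 20% to 60% it runs from 6% (d = 5%, R = 20%) to 63% (d = 40%, R = 60%). If the groups are split by the 7-visit rule, the share is d(1 − k·v) / {1 − v[(1 − d) + k·d]}. With v = 50% and k = 0.5 this is 7%, 14%, 27%, 39% and 50%. With v = 80% and k = 0 it is 21%, 36%, 56%, 68% and 77%.

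**Follow-up.** Section 9.1 gives a window of May 2012 through August 2019, which is 88 months. Seven years is 84 months. If treatment starts and follow-up both lie inside the window, only patients who started in the first 88 − 84 = 4 months could reach 7 years. Patients with 1 year of potential follow-up could have started in any of the first 88 − 12 = 76 months. If starts were spread evenly, that is 4/76, about 5% of them. A simple 7-year percentage over all of these patients counts many who could not yet have reached 7 years, which pushes the figure down, against the effect of the exclusion.

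**The case against.** The strongest reply has four parts.

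First, section 9.6 defines 1-year adherence by visits within a treatment year, so requiring a year on drug fits that definition, and the continued-treatment wording belongs to the secondary objective. This stands in part. A reader might infer that the 1-year figure is forced to 100%. It is not, because a completer without 7 consecutive visits counts as nonadherent. The result is still attendance among completers, while the stated objective carries no such limit.

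Second, the plan never says starters, and adherence among 1-year completers is a legitimate, openly stated population. That is fair for the 7-year question, provided the objective and the results say so. It does not rescue a 1-year adherence objective in a cohort chosen for 1 year of use.

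Third, the primary outcome in section 9.3 is the 7-year percentage. If section 9.6 means that 7-year adherence is assessed among first-year adherers, the exclusion does no harm to it when no early stopper met the visit rule. This stands, so it cannot be said that the primary outcome is necessarily inflated. The plan does not say which denominator applies.

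Fourth, section 9.2 hypothesises that few patients adhere for 7 years, and upward inflation works against that hypothesis. This also stands for the exclusion taken alone. The short follow-up window works in favour of the hypothesis, so the net direction is not settled.

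**Conclusion.** The concern holds in a limited form. As written, the plan leaves first-year stoppers out of the 1-year denominator and out of the nonadherent efficacy group, and out of the 7-year denominator if that is all eligible patients. Sections 8, 9.1, 9.3 and 9.8 do not disclose the consequence, and section 9.2 conflicts with the formal criteria.

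The size is unknown. With 5% to 40% assumed to stop in year 1, the 1-year figure is inflated by at most 1.05 to 1.67 times, and by less if some early stoppers met the visit rule. The effect of the exclusion on a 7-year figure over all eligible patients has the same range. Over first-year adherers it runs from none to 1.33 times on the values tried.

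Two stronger conclusions are tempting. One is that the reported 7-year percentage must be too high. Both the unstated denominator and the limited follow-up prevent that. The other is that the efficacy difference is biased in a known direction. That depends on why early stoppers stopped, which the documents do not say.

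**What to change.** **Preferred.** Define the cohort as all adult SpA patients whose first biologic was etanercept. Replace the 1-year treatment requirement in sections 9.2.1 and 9.2.2 with a first dose at least 1 year before the data cut. Apply the other-biologic exclusion only to use before etanercept was started, so that stoppers who switched are kept, and bring section 9.2 into line. Report 1-year adherence over all such starters, with early stoppers counted as nonadherent. Report 7-year adherence by Kaplan-Meier with administrative censoring. If only start dates or start years can be obtained, report a percentage restricted to patients who started at least 7 years before the data cut. Do not report a simple 7-year percentage that includes starters with less potential follow-up.

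The cost is one more registry query and a reanalysis, and probably a less favourable 1-year figure. On the registry coverage stated in section 9.2, early stoppers should be on record. Re-extraction may still prove impossible: section 9.3 lists no start or stop dates among the data obtained, section 10 describes the data as anonymised, and section 6 planned the end of collection for 01 October 2020.

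**If the data cannot be re-extracted.** Keep the cohort and restate the objective. Label the 1-year, 7-year and efficacy results *among patients who completed at least 1 year on etanercept*. Name the 7-year denominator and the status that splits the efficacy groups, and draw no conclusion about all starters. Add to section 9.8: *Patients who stopped etanercept within 1 year were excluded; the results do not estimate adherence among all patients who started etanercept.* This needs only changes to text and labels, and the price is narrower conclusions.

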9.3. Data Sources

Patients were identified from the rheumatology patient registry with a SpA diagnosis and information was obtained on patient demographics (age, gender), education-level (years), present smoking status, disease duration (years), current MTX and steroid therapy (yes/no), baseline BASDAI, and BASFI and last assessment of baseline BASDAI and BASFI.

Primary Outcomes: was the percentage of patients that have 7 year adherence on Enbrel.

9.4. Study Size

There was no pre-identified study-size sample. Patients that met the criteria were entered into the study.

9.5. Data Management

The structured data was exported into an Excel spreadsheet and then transferred to the SPSS database (version 23) for statistical analysis.

9.6. Data Analysis

All covariates will be summarized to get information about frequency distribution and mean, median or standard deviation. Numbers and percentages will be provided for dichotomous and polychotomous variables when performing descriptive analysis of categorical data. Means, medians, standard deviations, and interquartile range as appropriate will be provided for continuous variables when performing descriptive analysis of continuous data. Patients will be assessed for first-year adherence (first-year adherence is defined as patients having at least 7 consecutive visits in one year of Enbrel treatment), then the 7-year adherence will be assessed and the percentage of patients that achieve 7-year adherence will be calculated. The difference between adherent and nonadherent groups in baseline visit and last visit BASDAI and BASFI will be assessed for both groups.

The bivariate analysis will be conducted to determine if there is any association between the outcome and the exposure (the covariates). Unadjusted comparisons between groups of covariates and outcomes will be evaluated using appropriate tests: chi-squared test will be used for categorical variables, t-test will be used for continuous variables, and the Kruskal-Wallis test for non-parametric variables; p-values will be generated. The baseline variables considered demographic data, disease duration (years), methotrexate (yes/no), current steroid therapy (yes/no), present smoking (yes/no).

The difference in efficacy between adherent and nonadherent groups by using change from the baseline in BASDAI and BASFI at the last visit will be determined. P-value <0.05 will be considered statistically significant, without multiplicity adjustment for this post-hoc analysis.

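### First-year adherence is a visit count in a cohort already required to have a year on Enbrel, while 7-year adherence, the primary outcome, has no rule

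*Combined protocol and SAP*

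**What the plan says.** The primary objective in Section 9.1 is "1 and 7 years adherence of SpA patients on Enbrel". Section 9.3 narrows the primary outcome: it "was the percentage of patients that have 7 year adherence on Enbrel".

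The only operational rule is in Section 9.6 and covers year 1: "first-year adherence is defined as patients having at least 7 consecutive visits in one year of Enbrel treatment". For the longer horizon the same section says only "then the 7-year adherence will be assessed and the percentage of patients that achieve 7-year adherence will be calculated". It gives no visit count, permitted gap, stop-date rule or treatment of incomplete follow-up.

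For the secondary objective, Section 9.1 describes one side of the comparison as "the adherent group of patients (who continued Enbrel treatment". Section 9.6 then compares BASDAI and BASFI between adherent and nonadherent groups without saying how, or at which horizon, the groups are formed.

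Eligibility is by time on drug. Inclusion criterion 4 reads "Patients have at least 1 year on Enbrel", and exclusion criterion 2 removes "Use of etanercept for less than 1 year duration".

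**The concern.** Staying on a drug and attending clinic are different quantities. Section 9.1 points to the first and the year-1 rule in Section 9.6 uses the second. Because everyone in the cohort has at least a year on Enbrel, the year-1 rule cannot separate those who stopped from those who continued. It can only separate treated patients by how they attended.

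The primary outcome has the more basic problem. With no 7-year rule, two analysts holding the same registry could report different percentages. The same gap carries into the secondary objective, because adherence status also forms the efficacy groups. If attendance was related to disease activity, which is possible but not stated, grouping by visits could tie misclassification to BASDAI and BASFI, and the planned comparisons are unadjusted.

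**Working it through.** The plan states no expected adherence, visit schedule or sample size, so there is no figure to reproduce. The check sets the rules side by side and then shows what depends on unstated facts.

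**1. Three hypothetical patients, all eligible**

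| Patient | Section 9.6, year 1 | Section 9.1 description | 7-year status |
|---|---|---|---|
| On Enbrel throughout; longest year-1 run is 6 visits | Nonadherent | Continued | No rule |
| Started 2015, still on drug August 2019; 7 visits in a row in year 1 | Adherent | Continued | No rule; 7 years not observable |
| 7 visits in a row in year 1, stopped in year 3 | Adherent | Discontinued | No rule; not on drug at 7 years |

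The first and third patients change efficacy group according to the definition used. The second has no defined place at 7 years.

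**2. Year 1 under the Section 9.1 description.** Criterion 4 and exclusion criterion 2 leave only patients with a year or more on drug, so 1-year persistence is about 100% by construction.

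**3. What the visit rule demands.** Seven visits in 365 days need a spacing of at most 365/7 = 52 days, or 365/6 = 61 days if a day-0 visit counts. The interval is not given, so a range is shown, counting months 0 to 12:
- monthly: 13 possible visits; 7 is 7/13 = 54% and spans 6 months
- every 2 months: 7 possible visits; all are required
- every 3 months: 5 possible visits; the rule cannot be met

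**4. The word consecutive.** Assume n scheduled visits, each kept independently with probability p, and let q = 1 − p. For n from 7 to 14, the chance of a run of 7 or more is p^7 × [1 + (n − 7)q].

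| p | n = 12 (monthly) | Scored nonadherent, n = 12 | n = 8 (six-weekly) |
|---|---|---|---|
| 0.80 | 0.2097 × 2.00 = 42% | 58% | 0.2097 × 1.20 = 25% |
| 0.90 | 0.4783 × 1.50 = 72% | 28% | 0.4783 × 1.10 = 53% |
| 0.95 | 0.6983 × 1.25 = 87% | 13% | 0.6983 × 1.05 = 73% |

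If the 7 visits may fall in any order, the monthly pass rate is 98% or more at each p. These are illustrations for patients treated all year, not estimates for this registry.

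**5. Calendar.** The window runs "from May 2012 through August 2019". Taking 1 May 2012 to 31 August 2019, with treatment starting and follow-up ending inside it, gives about 7.3 years. Seven full years can be seen only for starts up to 31 August 2012, which is 123 days. Starts that allow 1 year run to 31 August 2018, which is 2,314 days. The share is 123/2,314 = 5.3% of eligible start dates. The share of patients may differ, because starts need not be evenly spread.

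**The case against.** The best defence is that the two descriptions concern different items. The Section 9.1 phrase is a parenthesis in the secondary objective, not a formal definition, while Section 9.6 operationalises first-year adherence. They can coexist. That is fair, but the link between them is still missing, and Section 9.1 is the only other description of the adherent group.

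Second, visits may have been the occasions on which Enbrel was supplied, so that attendance partly tracks exposure. The documents do not say so. If true, stating it with the schedule would answer part of the year-1 point, but not the missing 7-year rule.

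Third, the schedule figures are hypothetical. A quarterly clinic would hardly adopt a 7-visit rule, and the two-monthly result depends on counting a month-0 visit. This stands: the range shows sensitivity to unstated facts, not the size of an error.

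Fourth, a persistence rule is no cure if simply applied at both horizons. It is uninformative at 1 year, and at 7 years it would fail or drop anyone who started after August 2012, including those still on drug. This also stands and shapes the fix.

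Finally, a reader might infer that the whole adherence result measures attendance. The documents do not support that: it is shown for year 1 only, and a 7-year measure with no rule cannot be shown to measure anything in particular.

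**Conclusion.** The point holds in a limited form. As written, the year-1 rule can label patients still on Enbrel as nonadherent, which sits badly with the Section 9.1 description of the efficacy groups. The primary outcome lacks an operational rule, and the basis for the BASDAI and BASFI groups is unstated. These conclusions need no assumption beyond the text, except that visits are not the drug-supply events.

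The amount of misclassification is not derivable. The 13% to 58% range rests on an assumed monthly schedule and independent attendance. A reader might also infer that the efficacy comparison is biased in a known direction. The documents do not support this, since nothing in them links visit frequency to disease activity.

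**What to change.** In Section 9.6:

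1. Define adherence as persistence from Enbrel start to discontinuation or last treatment, in line with Section 9.1. Estimate 7-year persistence by Kaplan-Meier, censoring patients still on drug at the end of August 2019, and say how records that end earlier without a recorded stop are handled. Alternatively, restrict the 7-year percentage to patients who started early enough for 7 years of follow-up. Either result is conditional on having completed the first year.
2. State that 1-year persistence is about 100% by construction under the eligibility criteria and so is not an informative result here.
3. Form the efficacy groups on continued versus discontinued status. Do not count patients still on drug with under 7 years of possible follow-up as nonadherent.
4. Keep the 7-visit count as a descriptive attendance measure only. Apply a permitted-gap limit, with sensitivity limits, only if dated exposure records exist.

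The cost is revised wording and a re-derivation from start and last-treatment dates, with no new patients. Exclusion criterion 2 implies that treatment duration was known, but Section 9.3 lists no start or stop dates, so their availability must be confirmed. The 7-year estimate will be imprecise because few patients can be observed that long. Data collection was planned to end in October 2020, so the revised definition should be reported as a change made after the fact.
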